1. BMI
 - a. $\text{BMI} \geq 30 \text{ kg/m}^2$ for the obese WMEN and UF groups but body weight less than 350 pounds to accommodate the DXA scanner
 - b. $\text{BMI} \leq 25 \text{ kg/m}^2$ (and $\text{BMI} \geq 18.5 \text{ kg/m}^2$) for the lean WMEN group

2. Age ≥ 18 years. Minors under the age of 18 will be excluded because growth and pubertal issues are significant parameters that could affect our outcomes and also because the time requirements of the study are such that they would interfere with school schedules.
Participants must be healthy, as determined by medical history, physical examination, and laboratory tests.
3. Weight stable ($\pm 2\%$) for last 3 months

3. Exclusion Criteria:

Candidates will be screened by phone to exclude those with BMI ≥ 26 kg/m² and BMI ≤ 29 kg/m², significant health problems, including cancer, hypertension, diabetes, current and past 3-month use of certain prescribed medications, especially those that could affect body weight, such as antidepressants and stimulants as well as smoking, or excess alcohol (> 3 drinks/d). Women must not be pregnant or lactating, and be at least 1 year postpartum. Candidates with a history of psychotic disorder or hospitalization for psychiatric illness within the past 1 year will not be eligible. They will need to be weight stable for the past 3 months ($\pm 2\%$) and cannot be in treatment for obesity or currently receiving psychotherapy. Individuals who meet criteria according to the phone screen will be invited to come to the unit for a screening visit and their screening sheets are placed in a locked filing cabinet. Forms from potential volunteers who are ineligible are shredded.

4. Experimental Design:

Screening visit: Participants will arrive on the unit in a fasting state. Written informed consent will be obtained from the participant prior to any screening visits, study procedures or

treatments. The Principal Investigator or other designated qualified protocol investigators (listed on the protocol face page) will explain the study in language understandable to the subject.

Because there are both clinical and technical areas that comprise this protocol, we will ensure both areas are fully addressed to the subjects by the research team with a clinical and technical member present during screening and consenting. We have designated on the protocol face page which investigators will obtain informed consent for this protocol. The investigator signature on the informed consent will be signed by the principal investigator or a designated clinical investigator.

Sufficient time and opportunity will be given for discussion of the research as well as to answer any questions they may have, taking care to minimize or eliminate the perception of coercion or undue influence. The participant and the investigator will sign the current IRB-approved informed consent document. A witness will also sign the consent document to attest only to the validity of the signature of the subject, not the validity or quality of the consent. This visit will then include:

- Height, weight, and blood pressure measurements
- A physical exam with a medical history component, including questions about medications and alcohol/substance use history. Those meeting criteria for current substance abuse or dependence or current suicidal ideation will be excluded.
- Research chemistry profile, including complete blood cell count, serum creatinine, ALT, AST, GGT, TSH, fasting plasma glucose and HbA1c. If fasting glucose is ≥ 125 mg/dL or HbA1c > 6.5 and thus, suggestive of diabetes, volunteers will not be eligible for participation in this study and will be referred to their personal physician for follow-up care.
- A urine sample for urinalysis, drug screen, nicotine test, and pregnancy test (if female)

- Brief meeting with a study counselor who will review the diet requirements and other protocol requirements such as the food pick-up schedule, phone contacts and self- monitoring requirements. Physical activity will be assessed using the Physical Activity Recall (PAR) Questionnaire (Wilson et al., 1986).

Following the screening visit, the study staff will meet to discuss the volunteer's eligibility for participation in the study, as set forth by the inclusion and exclusion criteria (detailed above) and will contact him/her to set up the baseline visit if accepted into the study.

The main goal of this study is to determine whether or not there are differences in dietary adherence between lean and obese individuals and between two groups of obese individuals assigned different heart-healthy dietary prescriptions (weight maintaining diet [WMEN] vs. underfeeding [UF]). The experimental design is comprised of a 6-week outpatient heart-healthy dietary intervention with 2 clinic visits per week. To achieve our study goals we will measure the following:

Baseline Visit 1:

1. Weight, waist, thigh circumferences & vitals
2. Body composition using dual energy X-ray absorptiometry (DXA)
3. Breakfast
4. Behavioral Questionnaires
5. Psychological performance tests
6. Meet with study counselor to discuss weight maintenance diet instructions and study procedures

These parameters are described in detail below:

- Body composition by dual-energy X-ray absorptiometry (DXA): DXA will be used to accurately measure body composition. DXA is an X-ray device which non-invasively assesses both skeletal density and soft tissue composition by region with a precision of <1% for bone and 4-5% for soft tissue densities. Total body scan requires 10-50 minutes depending on the stature and thickness of the subject. The major limitation of the apparatus is the width of the scanning table. We validated the use of a half-body scan as an indicator of whole body composition in obese subjects who do not fit entirely on the scanning area. This half body method is valid for individuals weighing as much as 350 pounds (27). During the procedure, the subject is asked to lie flat on the table and to remain motionless, because the subject's movement can compromise the precision of the measurement during the scan. Proper subject positioning is also important. Once the proper alignment is determined, the subject's ankles and knees are loosely strapped to maintain the position. When the machine is turned on, a 188 mA current flows through the X-ray tube to produce X-rays. As the scan table arms move from the top of the subject's head downward towards the subject's feet, the shutter opens and a narrow beam of radiations projects upward through the table top and subject. After the scan, the arm clears the subject's feet, the scanner stops, and the source shutter closes. The software then calculates body composition in grams of fat tissue and lean tissue and percentage of body fat. The operator remains in the room with the subject during the scan.
- Psychological Assessment: We will administer a battery of behavioral questionnaires and psychological performance tests to assess constructs related to adherence, eating-related behaviors, personality and additional psychopathology. These assessments will be used to

determine predictors of adherence and weight loss. Scores will be related to outcome measures and may be used as covariates in data analysis.

- Behavioral questionnaires:
 - Gormally Binge Eating Scale (28): a self-report questionnaire to assess binge eating behavior. Subjects are asked to choose 1 response from a set of 4 possible choices in 16 instances. This scale can successfully discriminate among persons having no, moderate or severe binge eating problems
 - The Questionnaire on Eating and Weight Patterns - Revised (QEWP-R) (29): a self-report instrument used for diagnosis of binge eating disorder (BED), designed to describe both behavioral manifestations and feelings/cognitions surrounding a binge episode. Volunteers will be excluded from the study if they have purging behaviors or have anorexia nervosa.
 - Perceived Stress Scale (PSS) (31): a 14-item self-reported questionnaire used to assess stress and an individual's perceived ability to cope with such stress over the last 28 days
 - The Inventory for Depressive Symptomatology (IDS –SR)(32): a measure of depressive signs and symptoms, applicable to atypical depression which has been associated with overeating. Those who report suicidal ideation or have scores consistent with major depression will be referred for appropriate treatment and follow-up. The clinical research unit employs a licensed psychologist, but the Phoenix Indian Medical Center also has on-call behavioral health available 24 hours/day

- Barratt Impulsivity Scale -11 (BIS-11) (33;34): a self-report scale which contains 30 questions and has shown internal consistency across populations (34). There are 3 subscales of the BIS, which categorizes impulsivity into 3 main aspects and has 3 subscale scores: motor (acting without thinking), cognitive (quick decisions), and non-planning (present orientation)
- Power of Food Scale (PFS: (35;36): is a 15-item self-report measure of individual differences in the appetitive drive to consume highly palatable food, independent of homeostatic hunger
- The Social Problem-Solving Inventory - Revised (SPSI-R; (37): is a 52-item self-report measure that uses a 5-point Likert scale to assess problem solving abilities. It has 5 subscales: 1) Positive Problem Orientation; 2) Negative Problem Orientation; 3) Rational Problem Solving; 4) Impulsivity/Carelessness Style; and 5) Avoidance Style
- The NEO-FFI Neo-Five Factor Inventory (38): is a 60-question validated questionnaire to assess the five major dimensions of personality (Neuroticism, Extraversion, Openness, Agreeableness and Conscientiousness)
- Weight Efficacy Lifestyle Scale (WEL; (39)): a 20-item questionnaire to rate confidence in ability to avoid eating on a 10-point Likert Scale
- Treatment Self-Regulation Questionnaire (TSRQ; (40): to determine autonomous motivation (internal reasons for change) and controlled motivation (extrinsic reasons for change)
- The Three-Factor Eating Questionnaire (TFEQ) (77): a 51-item questionnaire composed of 3 subscales. These subscales measure dietary restraint (i.e., the cognitive control of eating, 21 items), disinhibition (i.e., the tendency to have an uninhibited

response to food, 16 items), and perceived hunger (i.e., the susceptibility of eating in response to subjective feelings of hunger; 14 items) using “true/false” or multiple-choice items.

- Emotional Appetite Questionnaire (EMAQ) (78): used to examine eating response to both positive and negative emotions and situations.
- The Childhood Trauma Questionnaire (CTQ; 120): is a 28-item self-report inventory that assesses abuse and neglect during childhood.
- Physical Anhedonia Scale (PAS) (85): a 61-item scale to assess sensitivity to reward (STR). It is designed to reflect the degree to which individuals take pleasure from, and are motivated to engage in, rewarding behaviors. High scores on this scale reflect the anhedonic end of the STR dimension while low scores reflect ‘hedonia’ or the enhanced ability to seek out and enjoy natural rewards.
- MacArthur Scale of Subjective Social Status (119): contains 2 ladders measuring subjective socio-economic status. Studies have indicated that ladder rankings are more powerful determinants of health-related outcomes than traditional measures of SES (121).
- U.S. Adult Food Security Survey Module: Six-Item Short Form: a 6-item self-report version of the original 18-item module for the assessment of food insecurity over the past 12-months. It classifies households into 3 categories of food security status according to the U.S. food security scale (120). It has been shown to identify food-insecure households and very low food security with reasonably high specificity and sensitivity and minimal bias compared with the 18-item measure (122) and shows significant association between food insecurity and obesity.

- Psychological performance tests:
 - Iowa Gambling Task (41;42): to evaluate decision-making. Subjects will be instructed to try to gain as much fake money as possible by drawing 100 selections from a choice of 4 decks of cards, while starting with a loan. The decisions to choose from the decks should become motivated by reward and punishment schedules inherent in the task. Two of the decks are disadvantageous, producing immediate large rewards but these are (after a pre-punishment phase of about 10–15 cards) accompanied by significant money loss due to extreme punishments. The other 2 decks are advantageous; reward is modest but more consistent and punishment is low.
 - Stroop Color Word Test (43): to assess selective attention. Words are presented on the screen in either a congruent (color screen with words printed in color) or incongruent set (color-word screen where the color and the word do not match [for example, the word “green” is printed in blue ink]). The subject has to either read the words or name the ink colors as quickly as possible within a time limit. A second Stroop task will be administered that will include food words that are printed in varying colors. Subjects will be asked to name the color rather than the name of the food.
 - Wisconsin Card Sorting Test (44): to examine cognitive executive functioning. Subjects are presented with 4 stimulus cards and 128 response cards. They are instructed to respond with response cards to match each of the 4 stimulus cards (based on either color, form or number, but directions are ambiguous), and are told if they are right or wrong. Once a certain number of correct answers are made, the sorting

- principle is changed without warning, requiring the subject to figure out the new sorting strategy
- Go/No Go Task (45): to examine inhibitory control. Subjects are required to press a key whenever a target stimulus is presented and to refrain from pressing the key when a non-target stimulus is presented
 - Meeting with study counselor: The counselor will review the weight-maintenance heart-healthy dietary prescription and provide the volunteer with 3 days of food. The volunteer will be instructed to eat only the foods provided, consume no additional foods, maintain their current levels of physical activity, and to keep track on a self-monitoring food record form.
 - Weight Maintenance Dietary Prescriptions:
 - Recent studies have found that using free prepared meals facilitated greater adherence (16) and weight loss compared with a control group (17). Therefore, because the primary aim of our study is to compare differences between lean and obese groups and WMEN versus UF diets (rather than investigate real-world learning), all food items will be provided by the CRU, primarily as prepackaged meals and snacks for the volunteers to take home (see Table 2 for sample menu).
 - All diets will have 20%, 30%, and 50% of daily calories provided as protein, fat and carbohydrate, respectively. They are designated as "heart-healthy" because they will be balanced diets, which are also low in cholesterol and saturated fat.
 - During the baseline week, all participants will be fed their weight maintaining energy needs (WMEN), equal to the number of calories calculated for each participant based on the WHO equation with an activity factor (1.3-1.5)(46;47), based on results from the PAR questionnaire.

- *Women:* 18 to 30 y: $EE = 13.3 \times \text{weight (kg)} + 344 \times \text{height (m)} + 35$
30 to 60 y: $EE = 8.7 \times \text{weight (kg)} - 25 \times \text{height (m)} + 865$
- *Men:* 18 to 30 y: $EE = 15.4 \times \text{weight (kg)} - 27 \times \text{height (m)} + 717$
30 to 60 y: $EE = 11.3 \times \text{weight (kg)} + 16 \times \text{height (m)} + 901$
- During the first week, and prior to randomization, all patients will come for 2 outpatient visits to be weighed
- If their weight changes by 2%, their caloric intake will be adjusted by 200 kcal accordingly

Baseline Visit 2:

1. Weight
2. Adjust calories by 2%, if needed

Outpatient Visits (6 weeks):

- *Randomization:* During the first outpatient study visit, participants will meet with a study counselor to discuss randomization assignment. They will be provided with 4 days of food and will again be instructed to eat only the foods provided, consume no additional foods, maintain their current levels of physical activity, and to keep track on a self-monitoring food record form. Additionally, they will be instructed on how to use the smart-phone system
 - Heart-Healthy Dietary Prescriptions:
 - Both the lean and obese WMEN groups will continue to eat the same number of calories that were calculated for them during the baseline weight maintenance period

- The obese UF group will be assigned a diet of 35% of the calculated energy needs
- *Weight and BP*: obtained at each visit
- *Meal pick-up*: meals will be prepared by the metabolic kitchen and picked up on a twice weekly basis
- *Meeting with Study Counselor*: Participants will meet 1x/week with a study counselor to review food records and dietary adherence. The counselor will rate the participants adherence and participant will rate his/her adherence to the dietary prescription and to behavioral aspects on a 5- point Likert Scale (0 = low; 5 = high). Counselors will also obtain a rating of subjective hunger over the last week on the same Likert Scale (0 = low; 5 = high) and assess change in physical activity. Sessions will last 15-30 minutes.
- *Assessment of Adherence*: Subjects will complete additional assessments of adherence:
 - 24-hour recall: this will be conducted by a member of the study staff other than the primary counselor to avoid bias
 - Computerized confessional: participants will complete a computerized battery of questions that will include a 24-hour recall with prompts to encourage recall of various foods possibly consumed at various times during the day. Questions about other weight and eating behaviors will be included. Data from this procedure will enable us to compare with the in-person interview version of the 24-h recall and assess reliability

Outpatient Adherence Contacts:

- 24-h recall by phone: a member of the study staff will call at a random time, 1x/week to conduct a 24-h food recall

- Ecological Momentary Assessment (EMA) using Smart-phones: participants will use Smart-phones to monitor adherence. In brief, EMA research techniques reflect repeated, real-time (momentary) assessment in the participants' typical environment (48). Recent studies have shown that anger predicted binge episodes ([name] et al., 2007) and overall negative moods were higher on binge days than on non-binge days (Wegner et al., 2002). Signal contingent recordings will be used, which involves respondents recording experiences whenever signaled at semi-random times throughout the day. Signals will occur two times/day: once between 8am and 3pm and once between 3pm and 9pm and will be randomly dispersed.

When signaled, volunteers will be asked:

- Since the last time you were signaled, have you eaten anything?
- If yes, did you eat the study food provided to you?
 - If yes, did you finish the food?
 - If no, which foods didn't you eat?
- Did you eat anything else (in addition to the food provided)?
 - If yes, what did you eat?
- Mood will be assessed using the short version of the Positive and Negative Affect Scale (PANAS, Watson & Clark, 1989). Each item will be rated on a 7-point scale (0, none; 3 moderately; 6 extremely; [name] 2007; Wegner et al., 2002)
- Phones will have a data service plan to allow for transfer of data from the phone to a stored network. GPS and/or other tracking systems will not be installed and volunteers will not be monitored or tracked via the smart phone. Participants will have the option of using their own smart phones if they already have one.

After completion of the 6-wk outpatient study, volunteers will repeat the following tests during their final outpatient visit:

Post-Intervention Visit:

- weight, blood pressure
- Lab work; CBC, Research chemistry profile, urine HCG (for females)
- Repeat DXA
- Repeat behavioral measures and psychological performance tests
- Final adherence measurement and exit interview

5. Patient monitoring:

5.1 Criteria for individual subject withdrawal:

Any subject experiencing (1) clinically apparent deterioration or severe side effects resulting from the dietary interventions or (2) who develops any medical problem that poses a safety risk for further participation will be withdrawn.

6. Data Analysis and Sample Size:

The design of this study will allow us to look at differences in levels of adherence to a heart-healthy dietary prescription in lean vs. obese individuals. We will also be able to compare adherence levels in obese individuals who are being fed a WMEN diet compared to an UF diet. Additionally, we will measure predictors of adherence and the relationship between adherence and weight loss.

Data Analysis:

Measuring Adherence: (see Appendix B): for all measures, adherence will be examined as a binary variable (adherent versus non-adherent). Each measure will be awarded 0 points if non-adherent and 1 point if adherent.

1. Attendance: two sessions per week: (adherent = attended; non-adherent = not attended; 12 possible total points over the study).
 - a. counseling
 - b. food pick-up
2. Food Diaries: volunteers will turn in diaries during their weekly counseling visit. For each weekly diary there will be three scores (18 possible total points over the study):
 - a. *Completion of records*: adherent = completed diary; non-adherent = missing or incomplete diaries
 - b. *Dietary Adherence to Foods provided*: adherent = consumed all; non-adherent = did not consume all
 - c. *Adherence to Additional Foods*: adherent = did not consume any; non-adherent = consumed additional foods
3. 24-hour recall in-person interview: once per week on day of counseling session. For each session there will be three scores (18 possible total points over the study):
 - a. *Completion of interview*: adherent = completed interview; non-adherent = did not complete interview
 - b. *Dietary Adherence to Foods provided*: adherent = consumed all; non-adherent = did not consume all
 - c. *Adherence to Additional Foods*: adherent = did not consume any; non-adherent = consumed additional foods

4. 24-hour recall using computerized confessional: once per week on day of counseling session. For each session there will be three scores (18 possible total points over the study):
 - a. *Completion of records*: adherent = completed interview; non-adherent = did not complete interview
 - b. *Dietary Adherence to Foods provided*: adherent = consumed all; non-adherent = did not consume all
 - c. *Adherence to Additional Foods*: adherent = did not consume any; non-adherent = consumed additional foods
5. 24-hour recall (telephone): once per week. For each phone session there will be three scores (18 possible total points)
 - a. *Completion of recall*: adherent = completed recall; non-adherent = did not complete recall
 - b. *Dietary Adherence to Foods provided*: adherent = consumed all; non-adherent = did not consume all
 - c. *Adherence to Additional Foods*: adherent = did not consume any; non-adherent = consumed additional foods
6. EMA recordings: there will be two contacts per day. For each contact there will be three adherence scores. To avoid having EMA be more heavily weighted in the total score, the total weekly score will be divided by 7 to obtain an average weekly EMA score (42 possible total points per week; 6 possible total average points):

- a. *Completion of recording*: adherent = completed recording; non-adherent = did not complete recording. We will define incomplete or missing entries as non-adherent for that day.
 - b. *Dietary Adherence to Foods provided*: adherent = consumed all; non-adherent = did not consume all
 - c. *Adherence to Additional Foods*: adherent = did not consume any; non-adherent = consumed additional foods
7. Additional Non-Intervention Related Adherence Measure (once per week. For each rating there will be 1 score (6 possible total points over the study): We will also track the arrival time for weekly counseling session as a measure of adherence that is not directly related to the study intervention. Appointment adherence will be scored as the arrival within 5 minutes of the scheduled time and actual arrival time will be documented as a continuous measure of adherence. This measurement will allow us to examine the relationship between adherence to the dietary protocol and adherence to "other" factors (e.g. punctuality) and it will be included in the total adherence score.
- a. Appointment adherence: adherent = arrived within 5 minutes of scheduled appointment; non-adherent = did not arrive within 5 minutes of scheduled appointment

Adherence Score: The above variables will be totaled up to calculate a total adherence score out of a possible 21 points during each week. A percent (%) adherence score will also be calculated by dividing the total score by the number of variables assessed (21) and multiplying by 100 ($[(\text{total}/21)*100]$).

Statistical Analysis:

For our primary hypothesis, a one-way ANOVA will be performed with total adherence score as the dependent variable and group status (lean WMEN, obese WMEN, obese UF) as the independent variable. In addition, linear regression models adjusted for covariates including age, sex, race, socioeconomic status (SES) and baseline weight or percent body fat will also be used to examine the relationship of adherence and behavioral factors. Correlations between adherence scores, behavioral test scores and weight, fat mass and fat free mass loss will be calculated. Pearson's r will be calculated for data that are normally distributed and Spearman's correlation will be used if the distributions are non-normal. This will be an intention to treat study such that everyone who completes the run-in phase will be included in the final analysis. Missing data will be completed using a multiple imputation method utilizing the SAS procedures, PROC MI and MIANALYZE. This method introduces variability into the imputed values to reduce the risk of a type 1 error. All tests will have a 2-sided Type I error of $p = 0.05$.

Power Calculation:

Sample size calculations are based on the number of individuals needed to demonstrate a significant difference in adherence scores over the 6-week intervention period between the 3 diet groups (lean WMEN, obese WMEN, obese UF).

We based our expected percent adherence score on a recent paper by Williamson et al (26) who observed 52% adherence in a group of obese dieters. Our maximum possible adherence score is 21 per week. To account for the increased adherence we expect to see because food is being provided in the study, we have increased the proposed adherence from the 52%

adherence observed in the POUNDS LOST study by an additional 10% and applied this increase in score across all 3 groups. Thus, assuming 62% adherence, we would expect a mean weekly score of 13 in the calorie restricted group. If we in addition, consider a smaller a meaningful difference between the groups of 3 points; (lean WMEN = 19, obese WMEN = 16, obese UF = 13), assuming the same SD = 6, with a calculated sum of squares of the means = 32, across 3 treatment groups with a mean 16 +/- SD = 6, alpha = 0.05, the proposed total of 20 subjects per group (total n = 60) would allow us to achieve a power of 0.793 (**see table 3a**). If we assume a larger difference between the groups 3.5 points; lean WMEN = 20, obese WMEN = 16.5, obese UF = 13), the proposed total of 20 subjects per group (total n = 60) would allow us to achieve a power of 0.906 (**see Table 3a**). Because the drop-out rate in weight loss intervention studies averages around 25%, we plan to recruit a total of 150 subjects (25 per group) to account for both screening failures and attrition, and to ensure 60 completers (**see Table 3b**).

7. Benefits:

This is a supervised dietary outpatient study being offered to lean and overweight/obese individuals. The prescribed diet is "Heart-healthy" and could improve metabolic and health outcomes in all 3 groups. In addition, those in the UF group who adhere to the diet may experience weight loss, which may lead to additional favorable future metabolic outcomes. All volunteers will receive information regarding some aspects of their health, including lab screening tests, a thorough physical examination, a measure of body fat, and an evaluation of their glucose tolerance status. The results of these tests will be available to the subjects and will be provided to their personal physician, if desired. Other expected benefits of this study include obtaining generalizable knowledge related to the difference in levels of adherence between lean

and overweight/obese individuals, which has not yet been examined. We will also gain knowledge about predictors of treatment adherence for weight loss and the relationship between adherence and weight loss. Moreover, we are proposing novel ways to measure adherence, which could be used in future studies. The information obtained from this study should be useful to scientists, physicians, and psychologists.

8. Human Subjects Precautions:

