Subject recruitment for this study will be through advertisement in local newspapers and through postings of the included flyers in various public places such as, but not limited to, libraries, public universities, hospitals, health clubs, and local health fairs. Additionally, advertisements may be placed in some national newspapers or websites (Craigslist) to reach a wider audience, particularly for the lean, weight-maintaining arm of the study. We aim to recruit 50% women for each study arm. A review of previous enrollment in our studies indicates that we typically have an even distribution of ethnic groups in our study samples (e.g. control versus treatment) even when the representation of ethnic categories is not equal. Thus, we expect to have at least 33% of volunteers represented by African American, Hispanic, Asian, or Native American groups in each of our study arms. We plan to enroll 60 individuals and in order to enroll this many, we will likely need to screen many more. We have therefore set our anticipated number to be screened at 180, equal to three times the number enrolled. For randomization, we will stratify the groups by gender and age, using a block design.

2. Inclusion Criteria:

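### The pre-randomisation food record and the stratification factors go unused in the primary analysis; using them would modestly sharpen the randomised obese WMEN-vs-UF comparison

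*Combined protocol and SAP*

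**What the plan says.** **Run-in week.** Under Baseline Visit 1 (section 4, Experimental Design), the counselor supplies 3 days of food on the weight-maintenance prescription. Volunteers are to eat that food only and "keep track on a self-monitoring food record form". Weight Maintenance Dietary Prescriptions places this before allocation: "During the first week, and prior to randomization, all patients will come for 2 outpatient visits to be weighed". All participants are on the same type of diet at this stage.

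**Allocation.** Section 1, Subjects and Recruitment: "For randomization, we will stratify the groups by gender and age, using a block design".

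**After randomisation.** Outpatient Visits repeats the same eating instruction and the same form. Measuring Adherence (section 6) then scores each weekly diary on three yes/no items: completion, foods provided and additional foods. These are 3 of the 21 weekly points. The score sheet runs from Week 1 to Week 6 and has no run-in column.

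**Analysis.** Statistical Analysis: "a one-way ANOVA will be performed with total adherence score as the dependent variable", with group as the only factor. It adds "linear regression models adjusted for covariates including age, sex, race, socioeconomic status (SES) and baseline weight or percent body fat", aimed at how adherence relates to behavioural factors. The Psychological Assessment section says of the questionnaire and performance-test results: "Scores will be related to outcome measures and may be used as covariates in data analysis". Run-in diary adherence is not named as a covariate anywhere.

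**The concern.** Comparing WMEN with UF among obese participants is one of the two comparisons in the primary goal. It is also the only one that randomisation can support, because nobody can be allocated to be lean or obese. With 20 per arm it is imprecise.

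A diary kept on a common diet before allocation is an early, partial reading of the outcome. Adjusting the randomised contrast for it introduces no confounding, and if it predicts later adherence it narrows the standard error. The same holds for the stratification factors: if they predict outcome, leaving them out of the model generally makes the standard error too large. What is at stake is precision only.

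**Working it through.** **Inputs.** The Power Calculation section gives means "lean WMEN = 19, obese WMEN = 16, obese UF = 13" on the weekly 21-point scale, SD 6 and 20 per group. Its second scenario is 20, 16.5 and 13. Statistical Analysis gives two-sided alpha 0.05. The correlation r between the run-in score and the six-week score is not in the documents, so it is an assumption, shown over a range.

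**1. The plan's own figure.** For the three-group F test, λ = n·Σ(μᵢ − μ̄)²/SD² = 20 × (9 + 0 + 9)/36 = 10, on 2 and 57 df. Power is 0.793, as stated and as in Table 3A. The second scenario gives 0.906, also as stated. (The text's sum of squares of 32 does not fit these means, which give 18; the tabulated power is nevertheless right.) The 0.793 is driven by the 6-point gap between lean WMEN and obese UF.

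**2. The randomised contrast, unadjusted.** SE = 6 × √(2/20) = 1.90. Noncentrality = 3/1.90 = 1.58 on 38 df. Power = 0.338. For a 3.5-point difference it is 0.436. By the normal approximation, 80% power needs about 63 per arm (3 points) or 47 per arm (3.5 points).

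**3. The same contrast, adjusted.** Residual SD = 6√(1 − r²). Estimating k covariate slopes inflates the variance on average by 1 + k/(37 − k): 1 + 1/36 for one covariate and 1 + 3/34 for three. Residual df are 37 and 35. The three-covariate columns take sex and age to add no prediction, with age as a single term. Difference 3 points:

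| assumed r | residual SD | SE, run-in only | power, run-in only | SE, run-in + sex + age | power, run-in + sex + age |
|---|---|---|---|---|---|
| 0 | 6.00 | 1.92 | 0.330 | 1.98 | 0.314 |
| 0.2 | 5.88 | 1.88 | 0.341 | 1.94 | 0.325 |
| 0.3 | 5.72 | 1.83 | 0.357 | 1.89 | 0.339 |
| 0.5 | 5.20 | 1.67 | 0.419 | 1.71 | 0.398 |
| 0.6 | 4.80 | 1.54 | 0.476 | 1.58 | 0.453 |

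Against 0.338 unadjusted, the run-in score alone adds about 0.02, 0.08 or 0.14 at r = 0.3, 0.5 or 0.6. With two unprognostic strata terms the gains are about 0.00, 0.06 and 0.11. If all three covariates are unprognostic, the loss is 0.338 − 0.314, or about 0.02. Even at r = 0.8 the run-in score alone gives 0.72 for a 3-point difference. For 3.5 points, power with the run-in score alone is 0.53 at r = 0.5 and 0.70 at r = 0.7; it passes 80% only near r = 0.8 (0.84).

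**4. What the run-in can measure.** The smartphone system is taught at the randomisation visit, and no recalls or computerised confessional are described for the run-in. That leaves the three diary items and attendance. The analysis set is everyone who completes the run-in, so run-in attendance can hardly vary within it. The usable covariate is therefore a 0-to-3 diary score.

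**The case against.** The strongest reply is that nothing here is wrong. An unadjusted ANOVA is valid and unbiased for randomised arms, and the plan specifies no pairwise test of obese WMEN against UF that adjustment could improve. The covariate is three yes/no items set against a 21-point weekly score over six weeks, taken from a week when food is supplied, so a ceiling is likely and r could be low. Adjusted regressions that include age and sex are already planned.

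Most of this stands, and it limits the size and priority of the point. It does not remove it. The planned regressions address adherence and behavioural factors and do not list run-in adherence. The WMEN-vs-UF comparison is in the primary goal whether or not a contrast is named.

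A reader might go further and infer that the gain is free because the data are already in hand. The documents do not support that. Volunteers are told to keep the form, but Baseline Visit 2 lists only weight and calorie adjustment, and diary hand-in is specified only for the weekly counseling visits. A reader might also infer that the run-in supplies a full baseline value of the outcome, or that attendance can be added to it; step 4 of the working shows otherwise.

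**Conclusion.** The point holds as a low-to-moderate priority efficiency improvement. For the randomised 3-point contrast, power of 0.34 would become about 0.36, 0.42 or 0.48 with the run-in diary score alone, or about 0.34, 0.40 or 0.45 with sex and age added and unprognostic, at assumed r of 0.3, 0.5 or 0.6. At r of about 0.2 or less there is no gain. These figures rest on the plan's SD of 6 and 20 analysed per arm, a linear covariate effect and an r that the documents do not give.

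Two stronger conclusions should not be drawn. The plan's analysis is not biased by the omission. Nor would adjustment rescue this contrast: for a 3-point difference it stays short of 80% power throughout the range examined.

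The case applies to the randomised contrast only. Between lean and obese WMEN, run-in adherence on the same type of diet is itself part of the difference sought, and adjusting for it could remove some of that effect.

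**What to change.** 1. State in the protocol that the run-in food record is handed in before the assignment is made known, and score it on the three existing diary items. Leave out attendance. Say how the two food items are scored when the record is missing.
2. Prespecify obese WMEN versus obese UF as an ANCOVA on total adherence score, with the run-in diary score, sex and age as covariates. State the form in which age enters.
3. State that lean versus obese WMEN is not adjusted for run-in adherence.

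**Cost.** One existing form is collected and scored once more per participant, and wording is added to the protocol and analysis section. The model uses up to three degrees of freedom, and power falls by up to about 0.02 if none of the covariates is prognostic. No new instrument or visit is needed, but the wording must be fixed before outcome data are analysed by group.
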